6.7 BASELINE, TIME WINDOWS AND CALCULATED VISITS

Measurements reported with date and time and taken prior to the start of administration of trial treatment are pre-treatment values. Measurements reported with a date only (and no time) and taken on the day of first administration of trial treatment are assigned as pre-treatment values. These pre-treatment values will be assigned to visits according to the nominal visit number as recorded on the eCRF or as provided by the laboratory.

Refer to Section 5.2 for baseline definitions for each applicable efficacy endpoint in this trial.

For safety endpoints, the baseline is defined as the last value prior to initiation of the maintenance treatment (Visit M1).

Analysis of AE data, concomitant medication or non-drug therapies will not be based on visits. Therefore, no assignment to time windows will be necessary.

Only one observation per time window will be selected for statistical analysis at a particular visit – the value which is closest to the protocol planned visit day will be selected. If there are two observations which have the same difference in days to the planned day, but which are not measured on the same day, the later value will be selected. If there are two observations on the same day, the later value will be selected.

For derivation of the last value on treatment, minimum value on treatment, and maximum value on treatment, all on-treatment values (whether selected in any time window or not; see Table 6.1: 1 for definition of the on-treatment period) will be considered. These will be derived for analysis of laboratory and vital signs data. For identification of potentially clinically significant abnormal laboratory values, all values (whether selected in any time window or not) within the on-treatment period will be considered.

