5.2.2 Vital signs

Vital signs evaluations will be performed at visits as shown in the [Flow Chart](#). This includes body temperature, pulse rate, systolic/diastolic blood pressure and respiratory rate. Respiratory rate, pulse rate, and blood pressure will be measured after patients have been sitting comfortably for at least five minutes. Measurement of vital signs should precede blood sampling to avoid the impact of blood sampling on the vital sign measurements. At dosing visits, vital sign evaluations will be performed pre-dose for both visits with i.v. and s.c. administration of study drug. At s.c. dosing visits, vital signs will be assessed at approximately 10 minutes after study drug administration. Also, at visit M1 and visit M2 (s.c. dosing visits) additional vital signs assessments will be performed approximately 60 minutes post-dose (i.e. 60 min. after last injection). At visits with i.v. dose administration, vital sign evaluations will be performed pre-dose and additional evaluations will be taken at 5 and 60 minutes post-dose

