6.2.2 Treatment period(s)

The treatment period is lasting from Visit M1 until End of Treatment (EOT) Visit.

Study related procedures during treatment period will be performed as specified in the [Flow chart 1](#) and [Flowcharts 2](#), in case patients develop an inflammatory flare or fistula relapse.

Pregnancy testing

Urine pregnancy testing for all women of child-bearing potential will be conducted on-site every 4 weeks at visits with study drug administration and must be negative to continue

treatment. More frequent testing should be done if required by the local regulation and / or authority or per investigator judgment.

The pregnancy testing should be done **prior to** study drug administration. A positive urine test must be confirmed with a serum pregnancy test.

Blood sampling

Blood sampling (e.g., for safety lab, []) should be done, if applicable, **prior to** study drug administration and **prior to** rectoscopy/proctoscopy. It is not required that patient is fasted prior to collection of the safety laboratory testing as indicated in [Flowcharts](#), but patient has to be asked and information will be collected on lab requisition form if patient was fasting or not 8 hours prior to blood sampling.

Endoscopy (Proctoscopy/rectoscopy/sigmoidoscopy/ colonoscopy or full ileocolonoscopy). It will be performed once per year during treatment period. Additionally, ileocolonoscopies have to be done in case of disease flare as indicated in [Flowchart 2](#).

Ileocolonoscopy can be performed instead of proctoscopy or rectoscopy if required per local guidelines (i.e. colon cancer screening or others) or routine clinical practice.

Stool sampling

A stool sample will be collected for faecal biomarkers.

Clinical monitoring after study drug administration:

Local tolerability at the administration site of the subcutaneous injection will be assessed by the investigator at the specified visits as noted in the [Flow Chart](#).

At all dosing visits vital signs will be assessed pre- and post-dose, please see [section 5.2.2](#) for further details.

Unscheduled visits

The patient may be asked for additional unscheduled visits due to safety reason at the discretion of the investigator or the sponsor, unless the patient has withdrawn his/her consent. The patient may also contact the site due to safety reason for an unscheduled visit. The unscheduled visit may include additional collection of blood samples for safety reasons and

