7.2.5 Safety analyses

Refer to [Section 7.2.2](#) for a description of the analyses of the primary endpoint, which for the present trial is a safety endpoint.

For the additional safety analyses described below, all treated patients will be included. In general, these additional safety analyses will be descriptive in nature and will be based on BI standards. No hypothesis testing is planned.

Statistical analysis and reporting of adverse events will concentrate on treatment-emergent adverse events, i.e. all adverse events occurring between start of treatment in this trial and the end of the REP. Refer to [Section 7.2.2](#) for the complete description of a treatment-emergent adverse event.

Frequency, severity, and causal relationship of adverse events will be tabulated by system organ class and preferred term after coding according to the current version of the Medical Dictionary for Drug Regulatory Activities (MedDRA) at database lock.

Laboratory data will be analysed both quantitatively as well as qualitatively. The latter will be done via comparison of laboratory data to their reference ranges. Values outside the reference range as well as values defined as clinically relevant will be summarised.

Laboratory data will be analysed descriptively with regard to distribution parameters as well as with regard to frequency and percentage of patients with abnormal values or clinically relevant abnormal values.

Vital signs, physical examinations, or other safety-relevant data observed at screening, baseline, during the course of the trial and at the end-of-trial evaluation will be assessed with regard to possible changes compared to findings before start of treatment.

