7.5 DETERMINATION OF SAMPLE SIZE

Given the descriptive nature of this trial, no sample size calculation has been performed.

Up to 20 patients who meet the entry criteria are planned for inclusion into this trial, rolling over from the parent trial. The parent trial's study cohort has a size of 20.

8. INFORMED CONSENT, TRIAL PROTECTION, PUBLICATION RECORDS, DATA POLICY, AND ADMINISTRATIVE STRUCTURE

The trial will be carried out in compliance with the protocol, the ethical principles laid down in the Declaration of Helsinki, in accordance with the ICH Harmonized Guideline for Good Clinical Practice (GCP), relevant BI Standard Operating Procedures (SOPs), the EU directive 2001/20/EC / EU regulation 536/2014 the Japanese GCP regulations (Ministry of Health and Welfare Ordinance No. 28, March 27, 1997) and other relevant regulations. Investigators and site staff must adhere to these principles. Deviation from the protocol, the principles of ICH GCP or applicable regulations as will be treated as “protocol deviation”.

Standard medical care (prophylactic, diagnostic and therapeutic procedures) remains the responsibility of the treating physician of the patient.

The investigator will inform the sponsor immediately of any urgent safety measures taken to protect the trial patients against any immediate hazard, as well as of any serious breaches of the protocol or of ICH GCP.

The Boehringer Ingelheim transparency and publication policy can be found on the following web page: trials.boehringer-ingelheim.com. The rights of the investigator and of the sponsor with regard to publication of the results of this trial are described in the investigator contract. As a rule, no trial results should be published prior to finalisation of the Clinical Trial Report.

The certificate of insurance cover is made available to the investigator and the patients, and is stored in the ISF.

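### SAP 6.7's same-day rule has no exception for planned post-dose vital signs, so any by-visit summary would set post-dose or undosed readings against a pre-dose baseline (minor)

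*SAP*

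**What the plan says.** **Schedule.** Protocol 6.2.2 states: "At all dosing visits vital signs will be assessed pre- and post-dose". Protocol 5.2.2 gives the times. At s.c. dosing visits, "vital signs will be assessed at approximately 10 minutes after study drug administration". At M1 and M2, "additional vital signs assessments will be performed approximately 60 minutes post-dose". At i.v. visits there is a pre-dose reading and two more, at 5 and 60 minutes. Several planned readings on one day are therefore the normal case at a dosing visit.

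**Selection rule.** SAP 6.7 states: "Only one observation per time window will be selected for statistical analysis at a particular visit". The value nearest the planned day is taken. For ties within a day, "If there are two observations on the same day, the later value will be selected". The section takes AEs, concomitant medication and non-drug therapies out of the windowing. It says nothing of the kind about vital signs.

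**Baseline and comparison.** SAP 6.7 defines the safety baseline as the last value before maintenance treatment starts at M1, which is a pre-dose reading. Under Protocol 7.2.5, vital signs observed during the trial "will be assessed with regard to possible changes compared to findings before start of treatment".

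**Extremes.** SAP 6.7 derives the last, minimum and maximum on-treatment values for laboratory and vital-signs data from all on-treatment readings, not only from the selected ones.

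**The concern.** A tie-break that takes the later of two same-day values is reasonable when the second value is a repeat. Here the readings on a dosing day are planned measurements of different things: the patient's state before the dose, and the response to it. Applied as printed, the rule drops the pre-dose reading at every dosing visit and keeps a post-dose one, while the baseline stays pre-dose.

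Two things are at stake in a by-visit summary. Change from baseline would combine any long-term change with any short-term effect of dosing. The short-term effect could not be separated out either, because the same visit's pre-dose reading is no longer in the summary. Protocol 11.2 (Global Amendment 2) gives safety after the first two s.c. doses as the reason for the added readings, and no analysis in the available SAP text compares a post-dose reading with its own pre-dose reading.

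**Working it through.** The documents state no figure to reproduce. The check applies SAP 6.7 to the readings scheduled in the protocol.

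**Step 1. Reading selected at each type of visit**

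| Visit | Planned readings that day | Selected under SAP 6.7 |
|---|---|---|
| M2 | pre-dose, 10 min, 60 min | 60 min |
| Other s.c. visits (M3 onward, F1 to F6) | pre-dose, 10 min | 10 min |
| i.v. reinduction | pre-dose, 5 min, 60 min | 60 min |
| Early EOT (no dose, Flow Chart footnote 12), flare or relapse confirmation, EOS | one, undosed | undosed |

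The printed rule speaks of two same-day observations. Where there are three, the table extends it in the natural way, to the latest.

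**Step 2. Visits affected**

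- Full seven-year schedule, M2 to M85 plus EOS: 85 − 1 = 84 dosing visits, plus 1, gives 85. Selected: 1 at 60 min (M2), 83 at 10 min, 1 undosed, 0 pre-dose.
- Dosing to week 144 (M37), then early EOT and EOS. This course is an assumption, matched to the highest exposure category in SAP 7.7. 37 − 1 = 36 dosing visits, plus 2, gives 38. Selected: 1 at 60 min, 35 at 10 min, 2 undosed, 0 pre-dose.
- Relapse after M13 with six F visits, then early EOT and EOS (also assumed): 12 (M2 to M13) + 1 confirmation + 1 i.v. + 6 + 2 = 22. Selected: 2 at 60 min (M2, i.v.), 11 + 6 = 17 at 10 min, 3 undosed, 0 pre-dose.

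The SAP describes the final analysis of a discontinued trial, so the second and third courses are the relevant ones. EOS is a weak example of an undosed on-treatment reading. Its planned day is 2466 − 2353 = 113 days after the planned last dose, one day past the limit of last dose plus 112 days in SAP 6.1. Early EOT and confirmation visits are the clearer cases.

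**Step 3. What the by-visit change would contain**

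For a dosing visit v,

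post(v) − pre(M1) = [pre(v) − pre(M1)] + [post(v) − pre(v)].

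The first bracket is change over the trial. The second is the response to that day's dose; call its mean d10 at 10 minutes and d60 at 60 minutes.

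- From M3 on, every s.c. visit carries the same kind of offset, d10. If d10 is stable over time, comparisons among these visits are sound, but their level relative to baseline is shifted by d10.
- M2 differs from later s.c. visits by d60 − d10 through timing alone. An i.v. visit carries the 60-minute response to an infusion.
- Undosed visits carry no offset, so they differ from neighbouring s.c. visits by −d10 through timing alone.

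The documents give no values for d10 or d60, so the size of the shift cannot be stated.

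**Step 4. The same courses with the pre-dose reading kept**

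The counts become 84 pre-dose and 1 undosed (full schedule), 36 and 2 (to week 144), and 19 and 3 (relapse course). No post-dose reading enters the by-visit change, and the second bracket disappears.

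**The case against.** The strongest objection is that no by-visit vital-signs table is visible. SAP 6.7 mentions vital signs only for last, minimum and maximum on-treatment values, and these bypass the window rule. Protocol 7.2.5 asks for possible changes from before treatment without specifying a by-visit mean change. The SAP's safety subsections after 7.8.1 and any window table are not in the available text, SAP 7.8 defers to sponsor standards, and SAP 7 says that part of the planned analyses will not be performed. This stands. The point is therefore conditional on a by-visit summary being produced and on no separate rule existing in the unseen text.

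Three stronger readings are tempting, and the documents do not support them.

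- *The by-visit course cannot show long-term change at any of up to 84 visits.* A reader might infer this from the mixed timing. But 83 of the 84 planned post-M1 s.c. visits share the 10-minute time point, so the course among them is broadly consistent. The 84 visits belong to the abandoned seven-year schedule.
- *A post-dose M1 reading would become baseline.* SAP 6.7 does class date-only readings on the first dosing day as pre-treatment. But nothing shows that clock times for vital signs are missing, and the main point itself needs an order within the day. This is a contingency to provide for, not an expected error.
- *Acute safety findings would be lost.* Clinically relevant vital-sign changes are recorded as AEs (Protocol 5.2.6.1.1), all individual values are listed (SAP 7), and the extremes include every on-treatment post-dose reading.

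None of this removes the defect in the printed rule. It is general in wording, several same-day readings are planned at every dosing visit, and a listing does not correct a summary table.

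**Conclusion.** The point holds, at minor severity. As printed, SAP 6.7 would never select the pre-dose reading at a dosing visit, so any by-visit vital-signs summary would compare unlike with like: a pre-dose baseline against readings at about 10 minutes at most visits, about 60 minutes at M2 and i.v. reinduction, and undosed readings at early EOT and confirmation visits. The main consequence is an offset from baseline of unknown size. Timing inconsistency is confined to the M2, i.v. and undosed visits. At most about 36 post-M1 dosing visits per patient are concerned.

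The effect is limited to descriptive safety summaries. The last on-treatment value does not pass through the rule either, although by definition it is the latest reading whatever its timing. The conclusion assumes that reading times or their order are recorded, that a by-visit summary is produced, and that SAP text not available contains no vital-signs rule. If such a rule exists, a cross-reference in 6.7 settles the matter.

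**What to change.** Add one paragraph to SAP 6.7:

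1. The same-day rule does not apply to planned post-dose vital signs.
2. On dosing days the pre-dose reading represents the visit, and by-visit change is taken from the M1 pre-dose baseline.
3. Post-dose readings are summarised by planned time point (s.c. 10 minutes, and 60 minutes at M1 and M2; i.v. 5 and 60 minutes) as change from the same visit's pre-dose reading.
4. Only if clock times are missing at M1, readings are classed as pre- or post-dose by planned time point.

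The cost is that paragraph and one small extra table. All readings are already scheduled, so neither data collection nor the visit schedule changes.

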7. PLANNED ANALYSIS

General Remarks

The format of the listings and tables will follow the BI guideline "Reporting of clinical trials and project summaries" (001-MCG-159) (7).

The individual values of all patients will be listed, including those collected during the off-treatment period. Listings will generally be sorted by country, centre number, patient number and visit (if visit is applicable in the respective listing). (see Section 7.8.1 below for details).

The following standard descriptive statistical parameters will be displayed in summary tables of continuous variables:

N number of non-missing observations

Mean arithmetic mean SD standard deviation

Min minimum Q1 lower quartile

Median median

Q3 upper quartile Max maximum

Statistical parameters will be displayed to a defined number of decimal places as specified in the BI guideline "Reporting of clinical trials and project summaries" (7).

Tabulations of frequencies for categorical data will include all possible categories and will display the number of observations in a category as well as the percentage (%) relative to the respective patient set (unless otherwise specified, all patients in the patient set irrespective of whether they have non-missing values or not). Percentages will be rounded to one decimal place. The category "missing" will be displayed only if there are actually missing values.

Considering the early termination of this long-term extension trial and the use of an abbreviated CTR (aCTR) for trial results reporting, part of the planned trial analyses will not be performed. For details, please refer to section 4.

7.2 CONCOMITANT DISEASES AND MEDICATION

Only descriptive statistics are planned for this section of the report by using the SAF only. The presentation of EIM is defined in Section 7.8.5.1.

Concomitant diseases (i.e., baseline conditions) will be coded according to the most recent version of MedDRA. Baseline here refers to the baseline of this current long-term safety trial.

Concomitant medication will be coded according to the most recent version of the World Health Organisation – Drug Dictionary.

Concomitant non-drug therapy will be coded according to the most recent version of MedDRA.

A medication/non-drug therapy will be considered concomitant to treatment, if it is ongoing at the start of this trial's treatment or starts within the on-treatment period (see Section 6.1 for a definition of study analysis periods).

7.3 TREATMENT COMPLIANCE

As described in section 4, reporting of treatment compliance is not required for an aCTR.

7.4 PRIMARY ENDPOINT(S)

The primary endpoint for this open label, long-term safety trial is a safety endpoint.

7.4.1 Primary analysis of the primary endpoint(s)

Refer to TSAP, Section 7.8.1.

7.5 SECONDARY ENDPOINT(S)

7.5.1 Key secondary endpoint(s)

None specified.

7.5.2 (Other) Secondary endpoints

Refer to TSAP, Section 5.2.2. for a description of the secondary endpoints. As described in Section 4, due to limitations in the CRF collection of data, it is not feasible to calculate either of the two secondary endpoints. A listing at the individual patient level showing the status of fistulas for each treated patient will instead be prepared.

7.7 EXTENT OF EXPOSURE

A table of total treatment exposure [mg] across the overall maintenance period will be summarized for the SAF for spesolimab s.c. and spesolimab i.v., respectively. For the time at risk, and for the total duration of exposure(weeks), data will also be tabulated as a frequency table with categorized treatment duration, (i.e., >0 to 48 weeks, >48 to 96 weeks, >96 to 144 weeks) for the SAF for 'Overall Speso' only.

7.8 SAFETY ANALYSIS

All safety analyses will be performed following BI standards. No hypothesis testing is planned.

7.8.1 Adverse events

AEs will be coded with the most recent version of MedDRA.

The analysis of AEs will be descriptive in nature. All analyses of AEs will be based on the number of patients with AEs and not on the number of AEs. System organ classes (if applicable) will be sorted according to the standard sort order specified by the EMA. Preferred terms (if applicable) will be sorted by total frequency (within system organ class).

For further details on summarization of AE data, please refer to "Analysis and Presentation of Adverse Event Data from Clinical Trials" (4) [KM Asset BI-KMED-BDS-HTG-0041] and "Handling of missing and incomplete AE dates" (3) [KM Asset BI-KMED-BDS-HTG-0035].

The analysis of AEs will be based on the concept of treatment emergent AEs. This means that all AEs will be assigned to either the screening period, the applicable on-treatment period, or the off-treatment period (i.e. follow-up) as defined in Section 6.1. Since only the start date of an AE is collected (without start time), any AE which occurs on the same day as the first maintenance treatment will be assigned to the respective on-treatment period.

Refer to CTP Section 7.2.2 for a description of the calculation of exposure-adjusted adverse event incidence rates (per the primary endpoint).

The AE summaries described below will be produced for the following treatment periods:

• The overall maintenance period [based on the SAF]

An overall summary of AEs will be presented. This overall summary will include the class of AESIs. Refer to CTP Section 5.2.6.1.4 for a description of what is considered as an AESI.

The investigator identified AESI will be captured from the eCRF and reported in the "Investigator reported AESI" table. In addition, user defined adverse event categories (UDAEC) identified through specific search criteria will be reported separately; the UDAEC applicable to this trial are stored centrally and will be referenced for this presentation.

Adverse Events classified as 'other significant' will be reported using an adaptation of the ICH E3 (6) and will include those non-serious and non-significant AEs which were reported with 'action taken = drug withdrawn' or 'action taken = reduced'.

Table 7.8.1: 1 Project MEDDRA search criteria for User Defined Adverse Events Categories (UDAEC)

User-defined AE category			
Label	Description		
Infections ALL	Combined search strategy based on the individual UDAECs for infections described below		
- Opportunistic infections	Narrow SMQ "Opportunistic infections"		
- Tuberculosis infections	BIcMQ "Infections": Narrow sub-search 8.2 "Tuberculosis related terms"		
- Serious infections	all serious events in SOC "Infections and infestations"		
- Severe infections	all events in SOC "Infections and infestations" of at least severe RCTC grade		
Hypersensitivity ALL	Combined search strategy based on the individual UDAECs for hypersensitivity described below		
- Anaphylactic reaction	Narrow SMQ "Anaphylactic reaction"		
- Angioedema	Narrow SMQ "Angioedema"		
- Hypersensitivity	Narrow SMQ "Hypersensitivity"		

TSAP for BI Trial No: 1368-0007 Page 23 of 29
Proprietary confidential information © 2022 Boehringer Ingelheim International GmbH or one or more of its affiliated companies

User-defined AE category			
Label	Description		
- DRESS, algorithmic	Based on broad SMQ "Drug reaction with eosinophilia and systemic symptoms" (SMQ code 20000225), defined using algorithm as follows:		
	A or (B and C and D) or (B and C and E) or (B and D and E)		
	where the categories A, B, C, D and E are defined categorisations of the PTs of the SMQ. For PTs of category A only narrow scope is used, for all other categories broad scope is used.		
	For identification of potential DRESS through the combination of adverse event occurrences within each of the categories B, C, D and E, adverse event start and end dates will be used. For the latter, potential DRESS is then identified if, within a 7-day period after occurrence of a relevant contributing event (assessed on each day between start and end date [inclusive] of the initiating event), there is at least one adverse event reported (based on start date only) from each of the other applicable categories within a specific combination of categories as described above (in parentheses).		
	If the end date is missing, the event is considered to be ongoing, and end date will be the last day of the applicable treatment period.		
- DRESS, narrow	Narrow SMQ "Drug reaction with eosinophilia and systemic symptoms", any event within category A only		
Malignancies ALL			
- Malignant tumours	Narrow Sub-SMQ "Malignant tumours" (Display also - Narrow Sub-SMQ "Haematological malignant tumours" - Narrow Sub-SMQ "Non-Haematological malignant tumours")		
- Malignancies excluding non-melanoma skin cancer (NMSC)	Sub-SMQ "Malignant tumours" excluding NMSC, where NMSC is defined as-broad Sub-SMQ "Skin malignant tumours" excluding HLT Skin melanomas (excl. Ocular)-		
Peripheral Neuropathy ALL			
- Guillain-Barré Syndrome	Narrow SMQ "Guillain-Barré syndrome" (SMQ code 20000131)		
- Peripheral Neuropathy	Narrow SMQ "Peripheral Neuropathy" (SMQ code 20000034)		

User-defined AE category			
Label Description			
- Demyelination	Narrow SMQ "Demyelination" (SMQ code 20000154)		

The exposure-adjusted incidence rate and frequency of patients with AEs will be summarised by treatment, primary system organ class and preferred term.

AEs which were considered by the investigator to be drug related will be summarised separately. Separate tables will also be provided for patients with SAEs, patients with AESIs, patients with AE leading to discontinuation of the trial, patients with other significant AEs and User-defined Adverse Event Categories (UDAEC) (see Table 7.8.1: 1). AEs will also be summarized by maximum or worst intensity based on the RCTC measure (see Section 5.4.1).

Listings for AEs by Primary System Organ Class and Preferred Term and SARS-Cov-2 infections at each individual level will be provided.

TSAP for BI Trial No: 1368-0007 Page 25 of 29
Proprietary confidential information © 2022 Boehringer Ingelheim International GmbH or one or more of its affiliated companies

TSAP for BI Trial No: 1368-0007 Page 26 of 29
Proprietary confidential information © 2022 Boehringer Ingelheim International GmbH or one or more of its affiliated companies

TSAP for BI Trial No: 1368-0007 Proprietary confidential information © 2022 Boehringer Ingelheim International GmbH or one or more of its affiliated companies

